9.4.1 Safety: Primary Endpoint

9.4.1.1 Primary Endpoint(s)

The safety of AZD7442 will primarily be assessed by:

- Incidence of AEs
- Incidence of SAEs
- Incidence of MAAEs
- Incidence of AESIs

The AE severity will be graded according to Appendix B and coded using the most recent version of the Medical Dictionary for Regulatory Activities. Adverse events will be presented for each dosing interval group by system organ class and preferred term. Summaries will include the number and percentage of participants reporting at least one event, number of events, and exposure adjusted rates, where appropriate.

An overview of AEs will be presented for each group, including the number and percentage of participants with any AE and SAEs. Summaries will present the relationship to IMP as assessed by the Investigator, maximum intensity, seriousness, and death.

A listing will cover details for each individual AE.

9.4.1.2 Other Safety Endpoint(s)

- Laboratory parameters (hematology, clinical chemistry, coagulation, urinalysis, and cardiac biomarkers)
- 12-lead safety ECG
- Vital signs (blood pressure, pulse rate, oral temperature, and respiratory rate)
- Physical examination

Laboratory assessments will be performed for hematology, clinical chemistry, coagulation, urinalysis, and cardiac biomarkers parameters. Laboratory parameters will be graded using the most recent version of the CTCAE.

Additionally, per the SoA (Section 1.3), all participants will be evaluated via ECG, vital signs, and a targeted physical examination. All parameters from laboratory, ECG, vital signs, and physical examination assessments will be summarized with descriptive statistics based on data type (continuous, categorical, etc). No hypothesis testing or CIs will be performed or calculated, unless otherwise specified.

9.4.2 Secondary Endpoints

9.4.2.1 Pharmacokinetic

Individual AZD7442 (AZD8895 and AZD1061) serum concentration data will be listed and tabulated, along with descriptive statistics. Pharmacokinetic parameters (eg, AUC, t_{1/2}) may be estimated using non-compartmental analysis if data permit. Potential correlation between PK exposure and efficacy/safety response may be explored. The serum AZD8895 and AZD1016 concentration data will be analyzed using a population PK analysis approach to characterize the PK for the different dosing intervals and will be reported in a separate report.

9.4.2.2 Antidrug Antibodies

The incidence of ADA to AZD7442 will be assessed and summarized by number and percentage of participants who are ADA positive by dosing interval group. The ADA titer will be listed by participant at different time points. The impact of ADA on PK, pharmacodynamic, efficacy, and association with AEs and SAEs, will be assessed.

Participants who receive an a different COVID monoclonal antibody than AZD7442, 30 days prior to entering the sub-study will be excluded from this analysis set. In addition, samples collected after a participant receives another COVID monoclonal antibody may be excluded.

[figure not shown]
9.4.2.3 Neutralizing Antibodies

Descriptive statistics for GMTs and GMFR will include number of participants, geometric mean, GSD, 95% CI, minimum, and maximum.

The GMT will be calculated as the antilogarithm of $\Sigma(\log_2 \text{ transformed titer/n})$, ie, as the antilogarithm transformation of the mean of the log-transformed titer, where n is the number of participants with titer information. The GSD for GMT will be calculated as the antilogarithm transformation of the standard deviation of the log-transformed titer. The 95% CI will be calculated as the antilogarithm transformation of the upper and lower limits for a two-sided CI for the mean of the log-transformed titers.

The fold rise is calculated as the ratio of the post-dose titer level to the pre-dose titer level. GMFR will be calculated as antilogarithm of Σ (log₂ transformed (post-dose titer/pre-dose titer)/n). The GSD and 95% CIs for GMFR will be calculated similarly to those for GMT.

Participants who receive an a different COVID monoclonal antibody than AZD7442, 30 days prior to entering the sub-study will be excluded from this analysis set. In addition, samples collected after a participant receives another COVID monoclonal antibody may be excluded.

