For participants who have not undergone a Day 366 visit in the parent study, the Day 366 assessments listed above should be performed at SS-D1. For participants who have already undergone the Day 366 visit in the parent study, only the SS-D1 assessments need to be performed. Day 366 assessments in the parent study will be used as baseline in the sub-study.

Perform 15 minutes (± 5 minutes) after both injections are complete.

If the urine pregnancy test is positive or indeterminate, a quantitative serum β-hCG will be performed by the central laboratory for confirmation. On SS-D1, a negative pregnancy test is required before the participant receives IMP.

- FSH will be analyzed at SS-D1 to confirm postmenopausal status only in women < 50 years of age who have been amenorrhoeic for ≥ 12 months. Until FSH is documented to be within menopausal range, the participant is to be considered of childbearing potential. For women aged ≥ 50 years, postmenopausal is defined as having a history of ≥ 12 months' amenorrhea prior to SS-D1, without an alternative cause, following cessation of exogenous sex-hormonal treatment.
- Weekly contact up to SS-D183 with participants to remind them to present to the study site for SARS-CoV-2 testing if they have qualifying symptoms. The Investigator will enquire about any COVID-19 symptoms from the past 7 days and other adverse events.

 Monthly contact with participants from SS-D183 to EOS, to assess overall safety. The Investigator will ask about any COVID-19 qualifying symptoms and cardiac events from the past month and other AEs. Participants should be reminded to present to the study site for SARS-CoV-2 testing if they have qualifying symptoms and to contact the site should they develop qualifying symptoms between each monthly contact.
- This test is not performed as part of the clinical study but must be available prior to enrollment.
- If a documented SARS-CoV-2 RT-PCR test is not available at screening, a rapid SARS-CoV-2 antigen test will be performed. Either test must be negative before dosing (see inclusion criteria in Section 5.1)
- Baseline sample, not a screening sample; results not needed prior to dosing.
- When test supplies are available, sampling should be performed.
- Perform immediately, 30 minutes (± 10 minutes) after both injections are complete, and prior to participant release (1 hour after IMP administration).

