• Participants assigned to the 18-month dosing schedule (Group 3) will be derived from a subset of participants at the USA sites in Group 1 and Group 2 in the sub-study (approximately evenly distributed between groups). This group will receive 2 doses of 600 mg IM AZD7442 at approximately 6 month intervals starting at SS-D183, following consent to the amended sub-study (see Figure 1), to align the dosing schedule per the FDA Fact sheet. This group will generate additional safety, PK, and immunogenicity data for longer-term repeat dosing time intervals of the long-acting AZD7442 formulation.

Evaluation of the safety, PK, and ADA immunogenicity of repeat dosing with AZD7442 will inform the following:

- Whether repeat dosing at different dosing intervals will maintain the serum concentrations of AZD7442 associated with protection against symptomatic disease in the parent study.
- Whether the safety profile and immunogenicity (ADA) profile after a repeat AZD7442 dose are comparable to the safety profile and immunogenicity profile observed after a single AZD7442 dose.

To provide safety data on AZD7442 for 5 half-lives, safety endpoints will be collected for 456 days after the last dose of IMP in Group 1 and Group 2.

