	medication/treatment	
	provider for management of chromaintenance. Primary care provide prescribe appropriate concomitato provide full supportive care and develop COVID-19 after receiving standard of care, including investigations.	ant medications prescribed by their primary care onic medical conditions and/or for health iders or, where appropriate, Investigators should nt medications or treatments deemed necessary and comfort during the study. Participants who ang IMP should be treated according to local stigational agents outside a clinical trial setting.
Restricted	 Products indicated for the prevention of SARS-CoV-2 or COVID-19 (including those under investigation or authorized under early access provisions) Hydroxychloroquine Chloroquine Ivermectin HIV protease inhibitors Convalescent COVID-19 plasma and sera Hyperimmune globulin 	 Note: For participants who develop SARS-CoV-2 infection or become hospitalized with COVID-19, receipt of approved/licensed treatment options are permitted and participants should be treated according to local standard of care, including investigational agents under Emergency Use Authorization or equivalent regulations. Use of hydroxychloroquine is acceptable if used chronically for autoimmune disease, and the dose is stable prior to Day 1 and up to Day 29. Use of chloroquine if used to treat a parasitic infection Use of ivermectin is acceptable if used to treat a parasitic infection HIV protease inhibitors are acceptable if used chronically for HIV infection, and the dose is stable prior to Day 1 and up to Day 29.
	Contraceptive methods	See Section 5.1 in the parent study protocol.
	Blood/plasma donation	Participants must abstain from donating blood or plasma from the time of informed consent and for 5 half-lives after dose of study drug; ie, one year.

COVID-19, coronavirus disease 2019; HIV, Human immunodeficiency virus; IMP, investigational medicinal product; SARS-CoV-2, severe acute respiratory syndrome-coronavirus-2.

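### The mandatory exclusion for another COVID antibody in the neutralizing-antibody summaries reaches back only 30 days from entry; earlier use is left to an optional rule with no criterion, so GMT and GMFR can be biased

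*Protocol*

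**What the plan says.** Post-dose nAb GMTs and GMFRs are a secondary endpoint (Protocol Section 3, Table 7). Section 9.4.2.3 defines the measure: "The fold rise is calculated as the ratio of the post-dose titer level to the pre-dose titer level". The same section has two exclusion rules for other antibodies.

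- **Mandatory, participant level.** Participants who receive "a different COVID monoclonal antibody than AZD7442, 30 days prior to entering the sub-study will be excluded from this analysis set".
- **Optional, sample level.** The next sentence adds that "samples collected after a participant receives another COVID monoclonal antibody may be excluded". It has no time limit and no criterion for use.

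The baseline is fixed elsewhere. The Schedule of Activities (Section 1.3) states that "Day 366 assessments in the parent study will be used as baseline in the sub-study". That visit has a window of ± 61 days, and a participant who has already completed it enters later at SS-D1.

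The entry criteria set a washout for COVID-19 vaccine (Section 5.2) but none for another antibody (Sections 5.1 and 5.2). Table 10 has a rule on further AZD7442 dosing after COVID-19 is treated with another monoclonal antibody, but does not say whether it covers use before entry. Table 14 defines no nAb analysis set. The supplied SAP covers the single-dose parent study, and its nAb evaluable set (SAP Section 5.7) has no rule on other antibodies.

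**The concern.** A participant given another COVID antibody more than 30 days before entry is not caught by the mandatory rule. If that product still circulates, it adds neutralizing titre to the pre-dose sample, which is the denominator of the fold rise, and a smaller amount to the early post-dose samples. The GMT is then too high and the GMFR no longer describes the response to AZD7442 alone.

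The starting point of the window adds to this. The 30 days run back from sub-study entry, but the sample that matters is the Day 366 sample. Suppose an antibody is given 40 days before SS-D1 and the Day 366 sample is taken 35 days before SS-D1. The participant passes the 30-day rule, yet the baseline was drawn 5 days after the antibody.

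The optional sentence could remove such samples, but nothing says when it will be used. In an open-label sub-study (Section 6.3) that choice could be made after titres are known.

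**Working it through.** The 30-day window is a rule with no stated derivation, so there is no planned figure to reproduce.

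**Inputs from the documents.** The only half-life information is for AZD7442. Section 4.2 states: "To provide safety data on AZD7442 for 5 half-lives, safety endpoints will be collected for 456 days". That gives 456/5 = 91.2 days. Table 10 gives "5 half-lives after dose of study drug; ie, one year" for blood donation, or 365/5 = 73 days.

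**Assumed inputs.** Half-life h of the other product: 14 to 91.2 days. Share of participants exposed: f. Factor by which carry-over raises an exposed participant's baseline: k. True fold rise: F = 20.

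**Step 1. How long is 30 days?** Number of half-lives = 30/h; fraction remaining = 2^(−30/h).

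| h (days) | Half-lives in 30 days | Remaining at day 30 |
|---|---|---|
| 14 | 2.1 | 23% |
| 21 | 1.4 | 37% |
| 28 | 1.1 | 48% |
| 73 | 0.4 | 75% |
| 91.2 | 0.3 | 80% |

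Across the range, an antibody given just outside the window leaves between about a quarter and four fifths of its level at entry.

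**Step 2. Effect on one exposed participant.** Take the participant's own baseline as 1 and the carry-over as c = k − 1, with titres adding and the baseline sample taken at SS-D1. At SS-D29, 28 days later, carry-over is c × 2^(−28/h).

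Observed fold rise = (F + c × 2^(−28/h)) / (1 + c).

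With F = 20, k = 50 and c = 49:
- h = 20: 2^(−28/20) = 0.379; (20 + 18.6)/50 = 0.77, which is 0.0386 of the true 20.
- h = 91.2: 2^(−28/91.2) = 0.808; (20 + 39.6)/50 = 1.19, which is 0.0596 of the true 20.

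**Step 3. Effect on the group.** The GMFR is a geometric mean, so the group multiplier is the individual ratio raised to the power f.

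| f | h = 20 | h = 91.2 |
|---|---|---|
| 1% | 0.968 | 0.972 |
| 5% | 0.850 | 0.868 |
| 10% | 0.722 | 0.754 |

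At h = 14 and f = 5% the multiplier is 0.842, so the result depends little on half-life. The simpler formula k^(−f) gives 50^(−0.05) = 0.82, but overstates the loss because it ignores carry-over in the post-dose sample.

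**Step 4. Effect on GMT, same inputs, f = 5%.** Baseline GMT is multiplied by 50^0.05 = 1.22. SS-D29 GMT is multiplied by (38.6/20)^0.05 = 1.03 at h = 20 and (59.6/20)^0.05 = 1.06 at h = 91.2. The ratios 1.03/1.22 and 1.06/1.22 return the GMFR multipliers of about 0.85 and 0.87.

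**Step 5. Reverse direction.** If the antibody is given after the Day 366 sample but more than 30 days before SS-D1, the baseline is clean and only the post-dose titre is raised. With F = 20 and carry-over at SS-D1 of 5 times the participant's own baseline, the individual fold rise is multiplied by (20 + 5 × 2^(−28/h))/20, which is 1.10 at h = 21 and 1.20 at h = 91.2. Fold rise is then overstated.

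**The case against.** The strongest reply is that the optional sentence already covers the problem. It is not limited to antibodies given during the sub-study, so a baseline sample taken 60 days after a pre-entry antibody falls within it. This is right as far as it goes. A reader might infer that 30 days is the whole rule, or that contaminated samples must be kept; the documents do not support either. What remains is that removal is discretionary and has no criterion.

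Second, a reader might take 5 half-lives as the protocol's own washout standard and find that the nAb rule breaks it. It does not. The two places that use 5 half-lives concern the length of safety follow-up and blood donation, both after AZD7442. They imply different half-lives and say nothing about other products. The shortfall in step 1 therefore rests on an assumed half-life.

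Third, exposure may be rare. Use before entry fell under the parent protocol, which is not supplied, and no sub-study SAP is available to show how the option would be applied. COVID-19 vaccination is permitted outside 14 days either side of dosing, so baselines may already be raised and a 50-fold increase may be too large. The sub-study tests no hypotheses (Section 9.1). These points limit the size of the problem and leave the gap in the rule.

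**Conclusion.** The concern holds for the nAb summaries. The one mandatory exclusion is short for a circulating antibody over the whole assumed half-life range and is counted from a date that need not be the baseline date. Everything earlier is left to an unspecified option. GMT is biased upward. GMFR is usually biased downward, but a uniform downward bias should not be inferred, because an antibody given between Day 366 and SS-D1 works the other way.

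The size cannot be fixed from the documents. At 5% exposed, a 50-fold raised baseline and a true fold rise of 20, GMFR is multiplied by about 0.85 to 0.87 (half-lives of 20 to 91 days). At 1% exposed it is about 0.97, so the effect is small if few are exposed. Half-life, exposure, baseline increase and true fold rise are all assumptions.

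Section 9.4.2.2 repeats the same exclusion wording for ADA, and a reader might carry the argument over. It does not carry: ADA is "summarized by number and percentage of participants who are ADA positive by dosing interval group", with no fold rise to distort, and the documents give no mechanism by which another product would change that incidence.

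**What to change.** In Section 9.4.2.3, replace both the 30-day window and the optional sentence with one mandatory rule for the nAb summaries:

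- exclude participants who received another COVID monoclonal antibody at any time from parent-study Day 1 to SS-D1;
- exclude samples taken after any later such antibody.

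This needs no product half-life, covers the gap between Day 366 and SS-D1, and leaves no choice to be made after titres are seen. Show the same GMT and GMFR summaries without the exclusion as a sensitivity analysis, with the number of participants and samples removed, so that the reader can see whether it matters.

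The cost is a wording change. Dates of medication are recorded in the sub-study (Protocol Section 6.5), and the parent study treats anything started on or after its dose as concomitant medication and lists it (SAP Section 13). The downside is that a few participants are lost from the nAb summaries only. The safety set is unchanged.

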9.5 Interim Analyses

One interim analysis is planned to be conducted in this repeat dose sub-study. The interim analysis is planned after a minimum of 50 participants who received AZD7442 on Day 1 of the parent PROVENT study have received a repeat dose of AZD7442 on SS-D1 and been followed until SS-D29 (ie, for 28 days after their second dose of AZD7442). The interim analyses will assess the primary safety endpoint and available secondary endpoints. Additional interim analyses may be conducted to generate additional data as required.

9.6 Data Safety Monitoring Board

The independent DSMB monitoring the PROVENT parent study will provide oversight, to ensure safe and ethical conduct of the sub-study.

The DSMB will make any necessary recommendations to the Sponsor based on their evaluations of emerging data. The first Data Review Meeting will occur in conjunction with the first interim analysis as specified in Section 9.5. Subsequent Data Review Meetings will be held in line with the DSMB Charter. The DSMB will also review sub-study progress and

monitor for evidence of harm resulting from AZD7442. If required, the DSMB will recommend temporarily stopping or termination of the sub-study.

For details on the DSMB, refer to Appendix A 5. Further details, composition, and operation of the independent DSMB will be described in a DSMB Charter.

9.7 Adjudication Committees

9.7.1 Morbidity Adjudication Committee

An independent Morbidity Adjudication Committee will provide an independent, external, systematic, and unbiased assessment of blinded data to evaluate whether the causes of death for participants are considered COVID-19 associated. All fatal events will be further assessed as part of safety evaluation. Further details of this adjudication will be provided in a separate Morbidity Adjudication Committee Charter.

9.7.2 Cardiovascular Event Adjudication Committee

An independent Cardiovascular Event Adjudication Committee will provide an independent, external, systematic, and unbiased assessment of de-identified data to systematically evaluate cardiovascular events. The adjudicated cardiovascular events will be included in descriptive analyses of safety data. Further details of the Cardiovascular Event Adjudication Committee composition, operation, and listings of preferred terms to identify events are provided in a separate Cardiovascular Event Adjudication Committee Charter.

10 SUPPORTING DOCUMENTATION AND OPERATIONAL CONSIDERATIONS

Appendix A Regulatory, Ethical, and Study Oversight Considerations

A 1 Regulatory and Ethical Considerations

- This sub-study will be conducted in accordance with the protocol and with the following:
 - Consensus ethical principles derived from international guidelines, including the Declaration of Helsinki and Council for International Organizations of Medical Sciences (CIOMS) International Ethical Guidelines
 - Applicable ICH GCP Guidelines
 - Applicable laws and regulations
- The protocol, protocol amendments, protocol addendum, ICF, IB, and other relevant documents (eg, advertisements) must be submitted to an IRB/IEC by the Investigator and reviewed and approved by the IRB/IEC before the sub-study is initiated.
- Any amendments to the protocol will require IRB/IEC and applicable Regulatory
 Authority approval before implementation of changes made to the study design, except
 for changes necessary to eliminate an immediate hazard to study participants.
- AstraZeneca will be responsible for obtaining the required authorizations to conduct the study from the concerned Regulatory Authority. This responsibility may be delegated to a CRO, but the accountability remains with AstraZeneca.
- The Investigator will be responsible for providing oversight of the conduct of the study at the site and adherence to requirements of 21 CFR, ICH guidelines, the IRB/IEC, European Regulation 536/2014 for clinical studies (if applicable), European Medical Device Regulation 2017/745 for clinical device research (if applicable), and all other applicable local regulations.

Regulatory Reporting Requirements for SAEs

- Prompt notification by the Investigator to the Sponsor of an SAE is essential so that legal
 obligations and ethical responsibilities toward the safety of participants and the safety of
 the IMP under clinical investigation are met.
- The Sponsor has a legal responsibility to notify both the local Regulatory Authority and
 other regulatory agencies about the safety of the IMP under clinical investigation. The
 Sponsor will comply with country-specific regulatory requirements relating to safety
 reporting to the Regulatory Authority, IRB/IEC, and Investigators.
- For all studies, except those utilizing medical devices, Investigator safety reports must be
 prepared for suspected unexpected serious adverse reactions (SUSAR) according to local
 regulatory requirements and Sponsor policy, and forwarded to Investigators as necessary.
 - European Medical Device Regulation 2017/745 for clinical device research (if applicable), and all other applicable local regulations

 An Investigator who receives an Investigator safety report describing an SAE or other specific safety information (eg, summary or listing of SAEs) from the Sponsor will review and then file it along with the Investigator's Brochure and will notify the IRB/IEC, if appropriate according to local requirements.

A 2 Financial Disclosure

Investigators and sub-investigators will provide the Sponsor with sufficient, accurate financial information, as requested, to allow the Sponsor to submit complete and accurate financial certification or disclosure statements to the appropriate regulatory authorities. Investigators are responsible for providing information on financial interests during the course of the study and for one year after completion of the study.

A 3 Informed Consent Process

- The Investigator or his/her representative will explain the nature of the sub-study to the
 participant or his/her legally authorized representative or equivalent representative as
 locally defined and answer all questions regarding the sub-study.
- Participants must be informed that their participation is voluntary, and they are free to
 refuse to participate and may withdraw their consent at any time and for any reason
 during the study. Participants or their legally authorized representative or equivalent
 representative as locally defined will be required to sign a statement of informed consent
 that meets the requirements of 21 CFR 50, local regulations, ICH guidelines, Health
 Insurance Portability and Accountability Act (HIPAA) requirements, where applicable,
 and the IRB/IEC or study center.
- The medical record must include a statement that written informed consent was obtained before the participant was enrolled in the sub-study and the date the written consent was obtained. The authorized person obtaining the informed consent must also sign the ICF.
- Participants must be re-consented to the most current version of the ICF(s) during their participation in the sub-study.
- A copy of the ICF(s) must be provided to the participant or the participant's legally authorized representative or equivalent representative as locally defined.

The ICF will contain a separate section that addresses and documents the collection and use of any mandatory and/or optional human biological samples. The Investigator or authorized designee will explain to each participant the objectives of the analysis to be done on the samples and any potential future use.

Participants will be told that they are free to refuse to participate in any optional samples or the future use and may withdraw their consent at any time and for any reason during the retention period.

A 4 Data Protection

Participants will be assigned a unique identifier by the Sponsor. Any participant records or datasets that are transferred to the Sponsor will contain the identifier only; participant names or any information that would make the participant identifiable will not be transferred.

- The participant must be informed that his/her personal study-related data will be used by the Sponsor in accordance with local data protection law. The level of disclosure and use of their data must also be explained to the participant in the informed consent.
- The participant must be informed that his/her medical records may be examined by Clinical Quality Assurance auditors or other authorized personnel appointed by the Sponsor, by appropriate IRB/IEC members, and by inspectors from regulatory authorities.

A 5 Committees Structure

The safety of all Sponsor clinical studies is closely monitored on an ongoing basis by Sponsor representatives in consultation with Patient Safety. Issues identified will be addressed; for instance, this could involve amendments to the CSP and letters to Investigators.

Data and Safety Monitoring Board (DSMB)

The same external DSMB from the PROVENT parent study will monitor and protect the safety of the participants throughout the sub-study. The DSMB members were selected for their expertise. The voting members of the DSMB are external to AstraZeneca, including the DSMB chair. Summaries of data will be prepared and provided to the DSMB. To minimize the potential introduction of bias, DSMB members will not have direct contact with the study site personnel or participants. The data for review will be outlined in the DSMB Charter and will be agreed to in advance by the DSMB members. The first Data Review Meeting will occur in conjunction with the interim analysis. Subsequent Data Review Meetings will be held in line with the DSMB Charter. Ad hoc meetings will be implemented if required. The DSMB will review safety data on a regular basis as set out in the DSMB Charter. Participant enrollment can continue during DSMB review of safety data. The available safety data for the participants will be evaluated by the DSMB. Safety summaries will be prepared prior to each Data Review Meeting. During the study, the benefit/risk assessment will be continuously monitored by the DSMB to ensure that the balance remains favorable.

The DSMB can recommend modifications of the sub-study protocol to enhance participant safety and to recommend temporarily stopping the study or early termination of the study if

there is strong evidence that AZD7442 or continuation of the study poses a safety concern to participants.

The independent DSMB monitoring the PROVENT parent study will provide oversight, to ensure safe and ethical conduct of the sub-study.

The DSMB will make any necessary recommendations to the Sponsor based on their evaluations of emerging data. The first Data Review Meeting will occur in conjunction with the first interim analysis as specified in Section 9.5. Subsequent Data Review Meetings will be held in line with the DSMB Charter. The DSMB will also review sub-study progress and monitor for evidence of harm resulting from AZD7442. If required, the DSMB will recommend temporarily stopping or termination of the sub-study.

For details on the DSMB, refer to Appendix A 5. Further details, composition, and operation of the independent DSMB will be described in a DSMB Charter.

Morbidity Adjudication Committee

See Section 9.7.1

Cardiovascular Event Adjudication Committee

See Section 9.7.2.

A 6 Dissemination of Clinical Study Data

A description of this clinical study will be available on

http://astrazenecagrouptrials.pharmacm.com and http://www.clinicaltrials.gov as will the summary of the study results when they are available. The clinical study and/or summary of study results may also be available on other websites according to the regulations of the countries in which the study is conducted.

A 7 Data Quality Assurance

- All participant data relating to the study will be recorded in the eCRF, unless transmitted
 to the Sponsor or designee electronically (eg, laboratory data). The Investigator is
 responsible for verifying that data entries are accurate and correct by electronically
 signing the eCRF.
- The Investigator must maintain accurate documentation (source data) that supports the information entered in the eCRF.
- The Investigator must permit study-related monitoring, audits, IRB/IEC review, and regulatory agency inspections, and provide direct access to source data documents.
- Monitoring details describing strategy (eg, risk-based initiatives in operations and quality, such as Risk Management and Mitigation Strategies and Analytical Risk-Based

Monitoring), methods, responsibilities and requirements, including handling of noncompliance issues and monitoring techniques (central, remote, or on-site monitoring) are provided in the relevant study plans.

- The Sponsor or designee is responsible for the data management of this sub-study including, quality checking of the data.
- The Sponsor assumes accountability for actions delegated to other individuals (eg, CROs).
- Study monitors will perform ongoing source data review to confirm that data entered into
 the eCRF by authorized site personnel are accurate, and complete; that the safety and
 rights of participants are being protected; and that the sub-study is being conducted in
 accordance with the currently approved protocol and any other study agreements, ICH
 GCP, and all applicable regulatory requirements.
- Records and documents, including signed ICFs, pertaining to the conduct of this
 sub-study must be retained by the Investigator for 15 years after study completion, unless
 local regulations or institutional policies require a longer retention period. No records
 may be destroyed during the retention period without the written approval of the Sponsor.
 No records may be transferred to another location or party without written notification to
 the Sponsor.

A 8 Source Documents

- Source documents provide evidence for the existence of the participant and substantiate the integrity of the data collected. Source documents are filed at the Investigator's site.
- Data entered in the eCRF that are transcribed from source documents must be consistent
 with the source documents or the discrepancies must be explained. The Investigator may
 need to request previous medical records or transfer records, depending on the study.
 Also, current medical records must be available.
- Definition of what constitutes source data can be found in the study monitoring plan.

A 9 Study and Site Start and Closure

The first act of recruitment is the first participant screened in the PROVENT parent study and will be the study start date. The Sponsor designee reserves the right to close the study site or terminate the study at any time for any reason at the sole discretion of the Sponsor. Study sites will be closed upon study completion. A study site is considered closed when all required documents and study supplies have been collected and a study site closure visit has been performed.

The Investigator may initiate study site closure at any time, provided there is reasonable cause and sufficient notice is given in advance of the intended termination.

Reasons for the early closure of a study site by the Sponsor or Investigator may include, but are not limited to:

- Failure of the Investigator to comply with the protocol, the requirements of the IRB/IEC
 or local health authorities, the Sponsor's procedures, or GCP guidelines
- Inadequate recruitment of participants by the Investigator
- Discontinuation of further IMP development

If the study is prematurely terminated or suspended, the Sponsor shall promptly inform the Investigators, the IECs/IRBs, the regulatory authorities, and any CRO(s) used in the study of the reason for termination or suspension, as specified by the applicable regulatory requirements. The Investigator shall promptly inform the participant and should assure appropriate participant therapy and/or follow-up.

Participants from terminated sites will have the opportunity to be transferred to another site to continue the study.

A 10 Publication Policy

- The results of this sub-study may be published or presented at scientific meetings. If this
 is foreseen, the Investigator agrees to submit all manuscripts or abstracts to the Sponsor
 before submission. This allows the Sponsor to protect proprietary information and to
 provide comments.
- The Sponsor will comply with the requirements for publication of study results. In
 accordance with standard editorial and ethical practice, the Sponsor will generally support
 publication of multi-center studies only in their entirety and not as individual site data. In
 this case, a coordinating Investigator will be designated by mutual agreement.
- Authorship will be determined by mutual agreement and in line with International Committee of Medical Journal Editors authorship requirements.

Appendix B Adverse Events: Definitions and Procedures for Recording, Evaluating, Follow-up, and Reporting

B1 Definition of Adverse Events

An AE is the development of any untoward medical occurrence in a patient or clinical study participant administered an IMP and which does not necessarily have a causal relationship with this treatment. An AE can therefore be any unfavorable and unintended sign (eg, an abnormal laboratory finding), symptom (eg, nausea, chest pain), or disease temporally associated with the use of an IMP, whether or not considered related to the IMP.

The term AE is used to include both serious and non-serious AEs and can include a deterioration of a pre-existing medical occurrence. An AE may occur at any time, including run-in or washout periods, even if no IMP has been administered.

B 2 Definition of Serious Adverse Events

A SAE is an AE occurring during any study phase (ie, run-in, treatment, washout, follow-up), that fulfills one or more of the following criteria:

- Results in death
- Is immediately life-threatening
- Requires in-participant hospitalization or prolongation of existing hospitalization
- Results in persistent or significant disability or incapacity
- Is a congenital abnormality or birth defect
- Is an important medical event that may jeopardize the participant or may require medical treatment to prevent one of the outcomes listed above

Adverse events for **malignant tumors** reported during a study should generally be assessed as **SAEs**. If no other seriousness criteria apply, the 'Important Medical Event' criterion should be used. In certain situations, however, medical judgment on an individual event basis should be applied to clarify that the malignant tumor event should be assessed and reported as a **non-serious AE**. For example, if the tumor is included as medical history and progression occurs during the study, but the progression does not change treatment and/or prognosis of the malignant tumor, the AE may not fulfill the attributes for being assessed as serious, although reporting of the progression of the malignant tumor as an AE is valid and should occur. Also, some types of malignant tumors, which do not spread remotely after a routine treatment that does not require hospitalization, may be assessed as non-serious; examples in adults include Stage 1 basal cell carcinoma and Stage 1A1 cervical cancer removed via cone biopsy.

Life-threatening

'Life-threatening' means that the participant was at immediate risk of death from the AE as it occurred or it is suspected that use or continued use of the IMP would result in the participant's death. 'Life-threatening' does not mean that, had an AE occurred in a more severe form, it might have caused death (eg, hepatitis that resolved without hepatic failure).

Hospitalization

Outpatient treatment in an emergency room is not in itself an SAE, although the reasons for it may be (eg, bronchospasm, laryngeal edema). Hospital admissions and/or surgical operations planned before or during a study are not considered AEs if the illness or disease existed before the participant was enrolled in the study, provided that it did not deteriorate in an unexpected way during the study.

Important Medical Event or Medical Treatment

Medical and scientific judgment should be exercised in deciding whether a case is serious in situations where important medical events may not be immediately life-threatening or result in death, hospitalization, disability or incapacity but may jeopardize the participant or may require medical treatment to prevent one or more outcomes listed in the definition of serious. These should usually be considered as serious.

Simply stopping the suspect drug does not mean that it is an important medical event; medical judgment must be used.

